4.1.1 ADJUSTMENT FOR MULTIPLICITY

TPL/008/2(v1.0)

Canolfan Ymchwil Treialon

Short title:	ISAP / SAP Template

We have used the O'Brien-Fleming type alpha spending method to adjust the interim analysis and final analysis level of significance. Adjustment for multiplicity of endpoints is not required because they are co-primary, therefore the resulting test procedure is an intersection-union test (Offen et al., 2007).

4.2 ADHERENCE AND PROTOCOL DEVIATIONS

4.2.1 DEFINITION AND ASSESSMENT OF ADHERENCE

Adherence to the algorithm will be recorded on the CRF and will capture instances where the treating clinician overrules the algorithm if they feel it is appropriate to do so. The ultimate responsibility for clinical care of the patient lies with the treating clinician; therefore, the cut-off boundaries for initiation times of antibiotics are not mandatory but are recommended guidance to aid clinical decision-making. The trial aims to assess whether the use of PCT can improve decision-making about which patients receive antibiotics and in what time period. Deviations from the algorithm will not be recorded as protocol violations.

4.2.2 PRESENTATION OF ADHERENCE

Descriptive statistics on adherence will be presented in a table, overall and by trial arm. The proportion of non-adherence and reason for non-adherence will be reported overall and as group-wise relative frequencies and percentages.

4.2.3 DEFINITION OF PROTOCOL DEVIATION

A protocol deviation occurs when the participant, study coordinator or investigator fails to adhere to significant protocol requirements, including eligibility violations, deviation from intervention or other non-adherence to the protocol. Due to the nature of the trial, the treating clinicians are allowed to overrule the algorithm when they feel it is appropriate. Protocol deviations will be classified as a deviation, protocol violation or serious breach and the impact on participants' rights, safety, wellbeing, and data integrity will be classified as major, minor or no impact. We will also record whether the deviation requires follow-up, and the PI will determine if a violation results in withdrawal of a participant.

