3. STUDY MATERIALS

3.1 TRIAL DESIGN

Parallel, two-arm, open-label, individually randomised controlled trial with two co-primary endpoints, an internal pilot phase, and group-sequential stopping rules for effectiveness. Participants are randomised in a ratio of 1:1 to PCT-guided assessment added to NEWS2 and local standard care, or NEWS2 and local standard care alone. The participant flow diagram (Figure 1) provides further details.

Canolfan Ymchwil Treialon

[figure not shown]

Figure 1: PRONTO trial participant flow diagram.

TPL/008/2(v1.0)

Short title:

ISAP / SAP Template

Canolfan Ymchwil Treialon

Short title: ISAP / SAP Template

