4.3 ANALYSIS POPULATION

The primary analysis population will include all participants with a completed 'record of consent' form (completed by participants with capacity, a personal consultee if a participant lacks capacity, or a nominated consultee if a personal consultee cannot be identified, or if the participant died prior to obtaining consent) regardless of protocol deviations and adherence, and according to their randomised allocations (intention to treat), with complete data for both co-primary outcomes. A

TPL/008/2(v1.0)

[figure not shown]
Canolfan Ymchwil Treialon

Short title:	ISAP / SAP Template

participant is considered to have complete 28-day mortality data if they have either been confirmed to have died within 28 days or they are known to have been alive at day 28. A sensitivity analysis will be performed including all participants for whom consent has been obtained with complete data for at least one of the co-primary outcomes.

A secondary/sensitivity analysis will estimate the complier average causal effect (CACE) to account for departures from the randomised intervention. For the purposes of this sensitivity analysis, we will define different analysis populations depending on the level of adherence with the PCT-guided algorithm (Figure 3):

- Patients randomised to PCT-guided care in whom a PCT test is done, and a PCT result is available
- Patients randomised to PCT-guided care in whom a PCT test is done, a PCT result is available, and the clinician has seen the PCT result
- Patients randomised to PCT-guided care in whom a PCT test is done, a PCT result is available, the clinician has seen the PCT result and followed the algorithm exactly.

Canolfan Ymchwil Treialon

Short title:	ISAP / SAP Template

Figure 3: Flow diagram defining the different analysis populations in participants randomised to PCT-guided care

We will include a 4 by 4 table comparing the outcomes of the clinical risk assessment and the risk stratification/algorithm (Appendix Table A1).

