5.5.1 LEVEL OF WITHDRAWAL

Some participants may wish to withdraw the use of the data upon first approach for deferred consent, following the intervention. If a participant provides deferred consent at this stage but subsequently withdraws from the trial, clear distinction must be made as to what aspect of the trial the participant is withdrawing from. These aspects could be:

- 1. Partial withdrawal from further data collection (questionnaires, clinical assessments)
- 2. Complete withdrawal from further data collection
- 3. Withdrawal of permission to use data already collected.

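### Section 4.2.3 lets the PI turn a violation into withdrawal without securing day-28 follow-up, which in effect undercuts the intention-to-treat rule in 4.3

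*SAP*

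**What the plan says.** Section 4.2.3 defines a protocol deviation broadly, "including eligibility violations, deviation from intervention or other non-adherence to the protocol", and grades each one as a deviation, a protocol violation or a serious breach. It then adds that "the PI will determine if a violation results in withdrawal of a participant". It gives no criterion for that decision, does not say whether withdrawal means from the intervention, from data collection or from use of the data, and does not mention continued follow-up.

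Other parts of the SAP bear on this:

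- Section 3.1: the trial is described as "Parallel, two-arm, open-label, individually randomised controlled trial with two co-primary endpoints".
- Section 4.3: consented participants are analysed "regardless of protocol deviations and adherence, and according to their randomised allocations (intention to treat), with complete data for both co-primary outcomes". Mortality data count as complete if "they have either been confirmed to have died within 28 days or they are known to have been alive at day 28".
- Section 6.2.1.2: the primary analysis is complete-case on both co-primary outcomes jointly.
- Section 4.2.1: "Deviations from the algorithm will not be recorded as protocol violations".
- Section 5.5.1: three levels of withdrawal, all for participants who choose to withdraw, with the instruction that "clear distinction must be made as to what aspect of the trial the participant is withdrawing from".
- Section 5.5.4: withdrawals are reported by arm, level, timing and, where available, reason.
- Section 6.3: multiple imputation is used only if more than 5% of primary outcome data are missing.

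**The concern.** Section 4.3 fixes the analysis set so that deviations play no part in it. Section 4.2.3 leaves open a route by which they can. The PI may withdraw a participant because of a violation. If that ends data collection before day 28, the participant no longer has complete mortality data and drops out of the joint complete-case analysis. The cause of the exclusion is then the deviation.

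The mortality outcome is the one exposed, because antibiotic initiation is settled within 3 hours of ED admission. The PI decides in an open-label trial, possibly once the clinical course is visible. Nothing in the SAP shields the decision from knowledge of the arm or of how the patient is doing. If those withdrawn differ in risk from the rest and the loss falls more on one arm, the mortality difference shifts, and the non-inferiority margin is only 2.5 percentage points.

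**Working it through.** **Can the sections be reconciled as written?**

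1. Does a violation lead to withdrawal? Under 4.2.3 it can, at the PI's discretion.
2. Does such a withdrawal have a defined level? No. Sections 5.5 to 5.5.3 describe withdrawal by the participant. Even when staff complete the form, they do so from what the participant tells them.
3. Does the sensitivity analysis in 6.2.5 bring the person back? Not for mortality. It uses complete cases for each outcome separately, so unknown day-28 status is still missing.
4. Does imputation bring the person back? Only if more than 5% of primary outcome data are missing. A selective loss of 1% to 2% of one arm would not trigger it by itself.
5. Does any section say that a PI-withdrawn participant is excluded or has data deleted? No.

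The exclusion is therefore possible and unguarded, but not prescribed.

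**Reproducing the plan's own figure (section 3.3).** Inputs: 15% mortality in both arms, margin 0.025, one-sided 5%, 90% power.

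n per arm = (1.6449 + 1.2816)² × 2 × 0.15 × 0.85 / 0.025² = 3494.05, so 3495 per arm and 6990 in total. The SAP states 7002, which is 0.2% higher. 7002 / 0.95 = 7370.5, so 7371, or 7372 as an even total, as stated. The design figures reproduce and are not in question.

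**Illustration of selective loss.** From the SAP: 7002 / 2 = 3501 per arm, control mortality 15%, margin 2.5 points, final critical value 1.654. Assumed, with no figure in the SAP: true PCT mortality 17.5% (at the margin), the fraction f lost, and the mortality m of those lost. The calculation uses a normal approximation and the final test only.

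- Observed mortality in an arm with true mortality p: (p − f·m) / (1 − f)
- SE = √[p₁(1−p₁)/n₁ + p₂(1−p₂)/n₂], using observed proportions and remaining numbers
- P(declare non-inferior) = Φ[(0.025 − RD)/SE − 1.654]

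With no loss, RD = 0.025 and P = Φ(−1.654) = 4.9%.

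Worked case, 2% of the PCT arm (70 people) lost at m = 30%: (0.175 − 0.02 × 0.30)/0.98 = 0.1724. RD = 0.0224 and SE = 0.0088, so (0.025 − RD)/SE = 0.289 before rounding, and P = Φ(0.289 − 1.654) = 8.6%.

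| Loss | m | PCT observed | Control observed | RD (points) | P(false non-inferiority) |
|---|---|---|---|---|---|
| None | – | 17.50% | 15.00% | 2.50 | 4.9% |
| 1% of PCT only | 30% | 17.37% | 15.00% | 2.37 | 6.5% |
| 2% of PCT only | 30% | 17.24% | 15.00% | 2.24 | 8.6% |
| 1% of PCT only | 15% | 17.53% | 15.00% | 2.53 | 4.6% |
| 2% of PCT only | 15% | 17.55% | 15.00% | 2.55 | 4.3% |
| 2% of both arms | 30% | 17.24% | 14.69% | 2.55 | 4.3% |

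The error rises only when the loss is both uneven between arms and concentrated in higher-risk patients. Within that case it is sensitive to m: at an assumed 50% mortality, losing 1% or 2% of the PCT arm only gives 10.0% or 18.4%.

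**The case against.** The strongest reply is that 4.2.3 concerns trial conduct while 4.3 decides who is analysed, and 4.3 is explicit. That stands against calling the two sections a direct contradiction. It does not close the gap, because 4.3 also requires complete outcome data and a conduct rule can remove them.

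A reader might infer an arm-specific route: a clinician overrules the PCT algorithm, the site logs it as a violation, and the PI withdraws the patient. The SAP does not support that. The clause is tied to a violation, 4.2.1 keeps algorithm deviations out of that class, and 4.2.3 itself says that clinicians may overrule. The listing of departures from the intervention in 4.2.3 could be worded more clearly, but it does not open this route.

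A reader might also infer that day-28 status is necessarily lost. That is not stated either. Table 2 takes mortality from medical notes up to 90 days, consent for records is separate from consent for contact (5.4), and the deviation log lists a tabulation of deaths in withdrawals by arm. Vital status may well be known for some of those withdrawn. This makes recovery feasible, but it is not a rule that returns them to the primary analysis.

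Eligibility is assessed before randomisation, so eligibility violations should arise about equally in both arms. Uneven loss would need uneven PI decisions, and the SAP offers no evidence of them. This stands and limits the size of the claim.

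Finally, follow-up after withdrawal may be covered in the protocol, which was not available for this review, and reporting by arm and reason is already planned. The analysis consequence still belongs in the SAP, since the SAP itself states the withdrawal rule.

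**Conclusion.** The point holds as a conflict in effect. The SAP gives the PI discretion to withdraw a participant after a violation, does not secure outcome collection, and uses a complete-case analysis that would then drop anyone with unknown day-28 status. That is at odds with the intent of 4.3.

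The size of any bias is unknown, because the SAP gives no number of PI-decided withdrawals. The rise from 4.9% to 6.5% or 8.6% is conditional on three assumptions: true mortality at the margin, loss of 1% or 2% confined to the PCT arm, and 30% mortality among those lost. It shows that a small selective loss would matter against this margin, not that one occurred. The point deserves correction because the remedy is cheap and does what 4.3 already intends.

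**What to change.** - Replace the withdrawal clause in 4.2.3 with a statement that a deviation or violation, including an eligibility violation, does not by itself end outcome collection or remove a participant from the intention-to-treat set.
- For anyone already withdrawn by a PI, take day-28 vital status and 3-hour antibiotic data from medical notes where consent allows, and include them in the primary analysis.
- Report PI-decided withdrawals by arm, separately from those chosen by the participant or consultee.

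Section 3.6 has data collection complete by November 2023, so the practical work is SAP wording, a check of the withdrawal log and retrieval from notes for the people concerned. No new patients are needed. The downside is that a few ineligible participants stay in the analysis, as 4.3 already intends.

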4.2.4 PRESENTATION OF PROTOCOL DEVIATIONS

The number and percentage of patients with major and minor protocol deviations will be summarised by treatment group with details of the type of deviation provided. Deviations that affect data integrity will be summarised in the final report.

4.3 ANALYSIS POPULATION

The primary analysis population will include all participants with a completed 'record of consent' form (completed by participants with capacity, a personal consultee if a participant lacks capacity, or a nominated consultee if a personal consultee cannot be identified, or if the participant died prior to obtaining consent) regardless of protocol deviations and adherence, and according to their randomised allocations (intention to treat), with complete data for both co-primary outcomes. A

TPL/008/2(v1.0)

[figure not shown]
Canolfan Ymchwil Treialon

Short title:	ISAP / SAP Template

participant is considered to have complete 28-day mortality data if they have either been confirmed to have died within 28 days or they are known to have been alive at day 28. A sensitivity analysis will be performed including all participants for whom consent has been obtained with complete data for at least one of the co-primary outcomes.

A secondary/sensitivity analysis will estimate the complier average causal effect (CACE) to account for departures from the randomised intervention. For the purposes of this sensitivity analysis, we will define different analysis populations depending on the level of adherence with the PCT-guided algorithm (Figure 3):

- Patients randomised to PCT-guided care in whom a PCT test is done, and a PCT result is available
- Patients randomised to PCT-guided care in whom a PCT test is done, a PCT result is available, and the clinician has seen the PCT result
- Patients randomised to PCT-guided care in whom a PCT test is done, a PCT result is available, the clinician has seen the PCT result and followed the algorithm exactly.

Canolfan Ymchwil Treialon

Short title:	ISAP / SAP Template

Figure 3: Flow diagram defining the different analysis populations in participants randomised to PCT-guided care

We will include a 4 by 4 table comparing the outcomes of the clinical risk assessment and the risk stratification/algorithm (Appendix Table A1).

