5.4 TIERED CONSENT PROCESS

Due to time constraints in managing suspected sepsis, patients will be randomised into either the standard care arm or interventional arm on diagnosis with suspected sepsis prior to consent being obtained. The participant will be approached within 72 hours of randomisation to complete the formal informed consent process. The process is described in the participant consent flowchart (PRONTO Protocol Version 3.1 dated 23/10/23; Section 9.3; Figure 2). During this process participants can consent to different aspects of the trial using a tiered consent approach.

Participants can agree to the following aspects of the study:

- 1. Information collected as part of the trial and data from medical records from the date of randomisation up to the date of consent can be used in the trial.
- 2. Data from medical records can be collected from the date of randomisation to 90 days after this date.
- 3. Participant to be contacted by research staff at day 28 and day 90 to ask about health, wellbeing and any further medical treatment they may have received.

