5.5 WITHDRAWAL/FOLLOW UP

If a patient does not wish to take part in any aspects of the trial, they will be withdrawn from the study and all clinical data up until that point will be removed from the study database. Participants have the right to withdraw consent for the use of clinical data collected in any aspect of the trial at any time. A participant's care will not be affected at any time by declining to participate or withdrawing from the trial.

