6.3 MISSING DATA

During data entry, validations have been written into the system to minimise the amount of missing data, however, missing data may still occur. The frequency and percentage of missing values will be reported overall and by arm. If missing primary outcome data is greater than 5% (as accounted for in the sample size calculation), we will conduct sensitivity analyses using multiple imputations (separately for both randomisation groups) (Sullivan et al., 2018). Missing data will be investigated for cause and extent and multiple imputation. The assumption of missingness at random (MAR) will be tested by analysing each baseline covariate in a separate logistic regression model to determine which (if any) are associated with the missingness of the primary outcome, and the associated p-values will be reported alongside the summary statistics. Missing observations will be replaced by multiple imputations by chained equations (MICE). A sensitivity analysis will be conducted on the primary analysis, including any baseline factors that were found to be associated with the

TPL/008/2(v1.0)

Canolfan Ymchwil Treialon

Short title:	ISAP / SAP Template

missingness of the primary outcome. Any changes to the assumptions made in the primary analysis will be considered in a sensitivity analysis.

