- Poisson regression analysis of days on IV/any abx in first 14 days
- Logistic regression analysis of whether IV abx was initiated within 12 hours

TPL/008/2(v1.0)

Canolfan Ymchwil Treialon

Short title: IS

: ISAP / SAP Template

- Logistic regression analysis of whether IV abx was initiated within 7-days
- Descriptive summaries of the following, to explore whether the treatment pathway may have changed between the arms
 - \circ ~ Time from triage (+/- randomization) to prescription of antibiotics
 - \circ ~ Time from triage (+/- randomization) to administration of antibiotics
 - \circ \quad Time between prescription and administration of antibiotics
 - \circ ~~ % blood cultures taken in first 24 hours (No other measure in CRF)
 - Broad spectrum Abx (Watch/Reserve) vs narrow spectrum (Access)
 - Initial Diagnosis Infection vs Not Infection
 - Cause of Death
 - Time to HDU/ITU admission
 - Broad spectrum Abx (Watch/Reserve) vs narrow spectrum (Access)
 - Abx choice Compare distribution of No Antibiotics> PO>IV Narrow>IV broad
 - % Microbiology tests in first 24 hours (Blood cultures only)
 - % Microbiology tests in first 24 hours (Any)
 - \circ ~~ % Any antimicrobial resistance detected, if yes which by %
 - Duration of antibiotics (initial course started within 24 hours of attendance)
 - Length of hospital stay
 - o % No antibiotics vs any antibiotics
 - % Late course of antibiotics (2-28 days)
 - Time to late antibiotics
 - % Readmitted to hospital
- Descriptive summary of the days on no abx, oral, iv broad, iv narrow, combination for each NEWS score and arm

05/09/24

- Tabulate first prescription within 24 hours from triage by arm
- Tabulate arm by final diagnosis with mortality in the cells infection vs non infection
- Tabulate deaths in withdrawals by arm

19/09/24

- Tabulate 28-day mortality in different algorithm adherence groups including the discordant groups (low clinical risk & high algorithm risk and vice versa) (unexpected vs expected PCT result)
- A logistic regression analysis of trial arm's effect on being alive and not readmitted at 90 days
- Subgroup analysis (as described in section 6.2.6) of grading of clinician conducting assessment
- Subgroup analysis (as described in section 6.2.6) of index of deprivation decile
- Tabulate time between 1st and 2nd assessment overall, by arm and by NEWS2
- Time series plot of ED crowding by site

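### The population labelled intention to treat is selected by consent completed after open-label allocation, and no planned analysis tests whether the mortality conclusion survives the exclusions

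*SAP*

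**What the plan says.** Section 3.1 describes the design as "Parallel, two-arm, open-label, individually randomised controlled trial with two co-primary endpoints". Under section 5.4, patients are randomised before formal consent: "The participant will be approached within 72 hours of randomisation to complete the formal informed consent process". Section 5.5.1 accepts that some may refuse use of their data at that first approach, when the intervention has already been delivered.

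Section 4.3 then fixes the primary set: "The primary analysis population will include all participants with a completed 'record of consent' form", analysed as randomised, with both co-primary outcomes complete, and labelled intention to treat. A nominated consultee may complete the form if no personal consultee is found, "or if the participant died prior to obtaining consent". For patients who want no part in any aspect of the trial, section 5.5 says "they will be withdrawn from the study and all clinical data up until that point will be removed from the study database".

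The wider sensitivity analysis in sections 4.3 and 6.2.5 still requires consent. The remaining analyses in 6.2.5 (CACE, arcsine-modified margin, repeat episodes) do not bring in patients without a form. Multiple imputation in 6.3 addresses missing primary outcome data. Sections 5.5.2 and 5.5.4 plan a CONSORT diagram and withdrawals by arm, level, timing and reason. Section 5.6.2 plans baseline summaries for all randomised participants. The SAP deviation log lists, as a post-hoc item dated 05/09/24, "Tabulate deaths in withdrawals by arm".

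**The concern.** Whether a randomised patient is analysed is decided after allocation, with the arm known. It also depends on early survival: a death before consent has a documented route into the analysis, whereas a living patient who refuses does not stay in. Selection of this kind raises observed mortality in both arms. If it acts more strongly in one arm, for example because PCT guidance alters early discharge or how patients see their care, it also moves the difference.

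The safety claim is a comparison against a 2.5-point margin. More removal in the control arm favours a finding of non-inferiority, and more removal in the PCT arm works against it. The label intention to treat tells a reader that post-allocation selection has been excluded, and it has not. The planned withdrawal tables would show unequal removal, but the plan does not say what that would mean for the conclusion.

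**Working it through.** **The plan's figure.** Section 3.3 uses 15% mortality in both arms, a 2.5-point margin, one-sided 5% and 90% power. The simple formula (1.645 + 1.282)² × 2 × 0.15 × 0.85 / 0.025² gives 3,495 per arm, or 6,990. With the variance constrained to the null (Farrington-Manning) it gives 3,501 per arm, or 7,002, which is the stated figure. For 5% dropout, 3,501 / 0.95 rounds up to 3,686 per arm, or 7,372, also as stated.

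**Inputs taken from the SAP.** 15% control mortality, 2.5-point margin, 3,501 analysed per arm (dropout already allowed for) and the final critical value 1.654.

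**Inputs that are assumptions.** The share removed in each arm, the mortality of those removed, and the share e who die before approach and are all kept.

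**Model.** Let p be true mortality, r the share of randomised patients removed and m their 28-day mortality. Observed mortality is (p − r·m) / (1 − r). P(non-inferior) = Φ((0.025 − RD) / SE − 1.654), with SE unpooled. With no removal and a true +2.5 points this returns 4.9%; with equal true rates it returns 90%.

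**Upper end: no removed patient dies.** Removal is a share f of 28-day survivors, so r = f(1 − p) and m = 0.
- Equal truth, 10% (control) v 15% (PCT): 0.15/0.915 = 16.39% and 0.15/0.8725 = 17.19%. The shift is +0.80 points and power falls from 90% to about 60%.
- Equal truth, 10% v 5%: 16.39% and 0.15/0.9575 = 15.67%. The shift is −0.73 points.
- True +2.5 points, 10% v 5%: 16.39% and 0.175/0.95875 = 18.25%. RD is 1.86 points, a shift of −0.64. SE is 0.00904, so P = Φ(0.709 − 1.654) = 17%.

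**Lower end: removed patients die at the rate of others alive at approach.** Removal is a share w of those alive at approach, so r = w(1 − e) and r·m = w(p − e), with e = 3% to 5%.
- Equal truth, 10% v 15%: shift +0.17 (e = 3%) to +0.27 points (e = 5%). Power is about 85% to 82%.
- Equal truth, 10% v 5%: shift −0.15 to −0.25 points.
- True +2.5 points, 10% v 5%, e = 3%: (0.15 − 0.012)/0.903 = 15.28% and (0.175 − 0.00725)/0.9515 = 17.63%. RD is 2.35 points and P = 6.9%. With e = 5%, P = 8.6%.

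**Sensitivity to the denominator.** Taking the upper-end percentages over all randomised patients, and not only 28-day survivors, means more removals. For 10% v 5% with equal truth the shift is 0.15/0.95 − 0.15/0.90 = −0.88 points, and false non-inferiority at a true +2.5 points is 20%. For 10% v 15% the shift is +0.98.

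**Two reference points.** Equal removal with equal true mortality gives a difference of zero in every version. To shift the difference by the full margin with no removal in one arm and no deaths among those removed, 1 − 0.15/0.175 = 14% would have to be removed in the other.

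**The case against.** The strongest reply is that the plan already limits and discloses the problem. Section 5.3 lets a patient or consultee refuse before randomisation, so some refusers never enter. The tiers in section 5.4 let a patient allow use of records while declining contact, and deletion under 5.5 applies to those who refuse every aspect. Withdrawals are to be reported by arm, level and reason. Section 4.3 states the consent restriction openly. Deletion on refusal is a consent obligation that a SAP cannot undo. All of this stands. It reduces the likely number removed and makes unequal removal visible, but it does not quantify the effect on the mortality conclusion.

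Three stronger readings are tempting and not supported:
- A reader might infer that the mortality result is biased. The SAP gives no removal rates, so unequal removal is a risk and not a fact.
- A reader might treat everyone removed as a 28-day survivor. The approach comes within 72 hours, so later deaths can occur among those removed, and the post-hoc tabulation of deaths in withdrawals presupposes this. Conversely, an early death is kept only if the form is completed.
- A reader might say that the 5% imputation trigger in 6.3 is confined to consented patients. The text does not say so. How often a patient leaves with no form depends on the protocol's consent flowchart, which is not shown here.

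**Conclusion.** The point holds as a gap in the plan. The primary set is a consented, complete-case subset, so the label in section 4.3 is inaccurate whatever the removal rates prove to be, and no analysis carries the exclusions through to the non-inferiority conclusion. For a 5-point removal gap, the plausible shift runs from about 0.15 to 0.3 points at the lower end to about 0.6 to 0.9 at the upper end, against a margin of 2.5. False non-inferiority is about 7% to 17% when removal is 10% in control and 5% in PCT, with removal at the upper end counted among survivors. These figures rest on assumed removal rates and on the assumed mortality of those removed; the only related rate in the SAP is the 5% dropout allowance. This should be fixed, but it does not by itself undermine the trial.

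Separately, section 5.6.2 promises baseline data for all randomised participants, which the deletion in 5.5 rules out for those who refuse every aspect.

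**What to change.** - **Section 4.3:** call the set modified intention to treat (consented, complete case).
- **Sections 5.5.2 and 5.5.4:** report by arm the number randomised but excluded, separating refusal, no completed form, and withdrawal of permission to use data. The count for no completed form is the main addition.
- **Section 6.2.5:** add a sensitivity analysis of 28-day mortality in all randomised patients that uses only these counts: (a) all excluded patients assumed alive at day 28; (b) a grid of arm-specific mortality for the excluded, extended to the point where the upper confidence bound crosses +2.5 points. State how far the non-inferiority conclusion holds.
- **Section 5.6.2:** reconcile with 5.5, for example by limiting baseline summaries to patients whose data may be used.

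Two alternatives would add nothing. Giving the excluded their own arm's observed mortality essentially reproduces the primary crude difference. Extending the imputation trigger to all randomised patients would ask for imputation in people whose clinical data have been deleted.

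The cost is some wording and one short calculation, with no clinical data from refusers. The robustness statement may turn out less favourable. As the deviation log already runs to December 2024, the analysis would now have to be logged as a late addition.
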